10.5 Planned Interim Analysis

N/A

10.6 Analysis Plan

All analyses will be conducted under the supervision of our senior statistician, [name] and METRC's senior economist, [name].

Specific Aims #1 and #2: Assessing Immediate and Long-term Improvements in Functional Performance and Self-Reported Outcomes. As described above, one-sided paired t-tests will be used to test for improvements in outcomes at a specified point in time after enrollment as compared to baseline. Differences in means between follow-up and baseline will be reported along with 95% confidence intervals.

To the extent possible, we will explore how improvement correlates with characteristics of the participants, the type and extent of their injury, baseline measures of impairment, and the percent of pre and post IDEO PT sessions attended (as we expect some variation in adherence to the PT regimen). Differences in improvement will be examined using stratified analyses and regressions where the change in outcomes is the dependent variable. We will also conduct the analysis including and excluding participants who complete less than 1/3 of the PT sessions.

Specific Aim #3: Documenting Patterns of Use and Satisfaction with the IDEO. This aim is largely descriptive in nature. To the extent possible, patterns of use and satisfaction will be compared with other studies reported in the literature. Also, variations in device satisfaction will be modeled as a function of patient characteristics and baseline measures of impairment using the appropriate regression techniques.

Specific Aim #4. Assessing the Economic Impact of PRIORITI. Relative to standard of care (SOC), the PRIORITI program may increase or decrease costs of care. Provision of the IDEO device, the associated rehabilitation program, need for special shoe wear, and any adjustments, repairs or replacements needed during the lifetime of wear represent added costs relative to SOC. However, the PRIORITI program could potentially reduce certain types of resource use and costs relative to SOC. For example, if the IDEO device offers greater mobility (without use of ambulatory aids) or reduced pain, participants might decrease follow-up visits or use of pain medications relative to standard of care. Use of the IDEO could also lead to fewer delayed amputations. Labor force participation, return to duty, and productivity of participants enrolled in

the PRIORITI program could also improve relative to SOC and this has economic benefit from both the patient and societal perspectives.

Our analysis of the costs and benefits of PRIORITI will involve two components: (1) analysis of costs and outcomes as observed during the 12-month study period; and (2) cost-effectiveness projected over the patient lifetime. 12 Month Costs and Outcomes Difference in one-year cost for the PRIORITI group relative to standard of care will be evaluated based on difference in means. Confidence intervals for difference will be estimated using a bootstrapping procedure that is robust for the anticipated right-skewed distribution of costs. If average cost is greater for the PRIORITI group, a cost-effectiveness ratio will be calculated using a metric such as incremental cost per unit change in Short Form Musculoskeletal Function Assessment (SMFA), or incremental cost per unit change in VR-12.

Lifetime Cost-Effectiveness. If superior to standard care, the PRIORITI program could have a major impact on the patient's long-term functional status and quality of life. To gain insight on this proposition, a cost-effectiveness model will be constructed that simulates the long-term course for two identical patient cohorts, IDEO and standard of care. Model parameters will be derived from the study data, literature review, and expert opinion. Markov modeling will be used in order to characterize patient health state over time. For example, a small portion of patients who initially undergo limb reconstruction, later elect amputation. This would represent a change of "health state" in a Markov model and the probability of transition from the "limb reconstruction state" to "amputation state" will be derived from literature review. Similarly, patient preference (utility) for various health states associated with recovery from traumatic injury will also be estimated and used to calculate quality-adjusted life years, to be derived using the VR-6D. Overall findings of this analysis will be stated in terms of incremental cost per quality adjusted life-year for PRIORITI relative to standard of care.

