Specific Aim #3: To document patterns of device use, use of ambulatory aids, shoe wear and patient reported satisfaction associated with the IDEO. Participants will be asked about their satisfaction with comfort, cosmesis, ease of use, and durability. As this is primarily a descriptive analysis, no hypotheses will be tested.

Specific Aim #4: To assess the economic impact of the PRIORITI program by (i) measuring one-year costs associated with participation in PRIORITI and compare these costs to those projected under standard of care; and (ii) estimating lifetime cost-effectiveness of the PRIORITI program relative to standard of care. As this is primarily a descriptive analysis, no hypotheses will be tested.

Study design: The effectiveness of the PRIORITI program will be evaluated using a before-after

study design where participants serve as their own controls.

Study duration: 3 years (6 month planning and training, 10 month accrual, 12 month final follow-up, 8 month analysis and writing).

Sample size: 90 participants will be consented to participate in this study.

Number of study sites: 3 Military Treatment Facilities (MTF's).

Inclusion criteria

1. Ages 18-60
2. Currently one or more years out from a traumatic unilateral lower extremity injury at or below the knee
3. Healed fractures and able to fully weight bear
4. Evidence of either:
 - a. Weakness of ankle dorsiflexors and /or plantarflexors resulting from leg injury (defined as less than 4 out of 5 on manual muscle test)
 - b. Limited ankle dorsiflexion (< 10 degrees) and /or limited ankle plantarflexion (< 20 degrees) resulting from leg injury
 - c. Mechanical pain with loading to hindfoot/midfoot (\geq 50 mm on a 0-100 mm visual analogue scale assessing average daily pain)
 - d. Ankle or Hindfoot fusion or candidate for ankle or hindfoot fusion
 - e. Candidate for amputation secondary to ankle/foot impairment

Exclusion criteria

1. Ankle plantarflexion or dorsiflexion weakness as a result of spinal cord injury or central nervous system pathology.
2. Non-ambulatory
3. Surgery on study limb anticipated in next 6 months
4. Medical or psychological conditions that would preclude functional testing (ex. severe traumatic brain injury, stroke, renal failure, heart disease, severe anemia)
5. Neurologic, musculoskeletal or other conditions affecting contralateral extremity preventing the study of a healthy control limb
6. Unable or unwilling to participate in two 4-week PT programs
7. Pregnancy

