- **Use and Satisfaction with the IDEO and Related Services.** At T2 (following completion of the physical therapy program), and at T3 and T4, each patient will complete a brief battery of questions to assess their use and overall satisfaction with the IDEO™ and related services. We will include both the Orthotics and Prosthetics Users' Survey (OPUS) ⁸¹⁻⁸² and elements of a survey developed at the Center for the Intrepid (designed specifically for comparing the satisfaction of the IDEO with other braces) ²². The OPUS was developed by Heinemann et al. using well established contemporary measurement technology for instrument development. The OPUS consists of an 11-item measure for satisfaction with *devices* and a 10-item measure for satisfaction with *services*. Items pertaining to device satisfaction include: weight, comfort, pain associated with use, ease of use, cosmesis, durability, fit and effect of the device on clothing (i.e., dimensions). Items used to measure satisfaction with services, include wait time, respect, communication, consumer's input, team approach, and training with the device. Lastly, participants will be asked if they ever considered amputation of their injured limb, if so, why, and if they now favor limb salvage or amputation.

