7. STUDY TREATMENTS

The PRIORITI intervention consists of two components: (1) custom fitting of the IDEO; and (2) the Return to Run physical therapy program designed specifically for recipients of the IDEO. Each is described below together with specifics regarding the training of Study Site staff to ensure fidelity of the intervention across sites.

All braces will be fabricated by trained Certified Prosthetist/Orthotists (CPOs) at each participating MTF. Training for fabrication of the IDEO is described below. The two participating study MTF sites will each identify 1-2 physical therapy assistants and 1 CPO and 1 O&P tech who will provide the services necessary for measuring, fabricating and fitting the IDEO and providing the PT. Only PTAs and orthotists who have been trained for the study (see below) will be allowed to provide services to PRIORITI participants.

7.1 Fabrication and Fitting of the IDEO. The IDEO design for this study will be the modular version, since it has the advantage of modifying alignment in a simpler manner, adjusting strut stiffness for limitations or gains of individuals, and limiting fabrication responses needed for fissuring or fracturing of components of the device with use. The IDEO is constructed primarily of laminated, reinforced carbon fiber to withstand high impact forces and cyclical loading. The main components of the IDEO are the proximal cuff, strut, and foot plate. These components are described in further detail in Appendix J. The IDEO is a class 1 exempt device. A provisional patent was filed in April, 2011 by [name], CPO in conjunction with the United States Government, as represented by the Secretary of the Army (Application Serial No. 61/518,801).

The team at the Center for the Intrepid (CFI) will train the CPOs from the other two military treatment facilities in IDEO fabrication. Training will consist of a 6-8 week internship working with the San Antonio team to learn the processes of measurement, fabrication, and fitting of the brace. Training materials will be developed through this process and used in subsequent training sessions. Once able to replicate the process, the CPOs will return to WRNNMC and NMCS D to implement the program at their institutions

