10.2 Sample Size Considerations

A total of 85 patients will be consented and enrolled by the military core METRC centers (approximately 25-30 from each center); data collected from these participants will be used to test the research hypotheses.

We anticipate a low dropout rate (<5%) because highly motivated individuals will self-select themselves into the program. We will also provide a modest compensation to participants who are not on active duty for their time and travel. For power calculations we assume we will have complete follow-up data on 80 of the 85 participants who enroll. All functional and satisfaction outcomes are continuous. In Specific Aim 1a and Specific Aims 2a and 2b, we plan to test for improvements in outcomes at a specified point in time after enrollment (8 weeks for Specific Aim 1a and 1 year for Specific Aims 2a and 2b) as compared to baseline. One-sided paired t-tests will be used. Differences in means between follow-up and baseline will be reported along with 95% confidence intervals. The proposed sample size yields 80% power to detect an effect size (mean of the difference in outcomes between follow-up and baseline divided by the standard deviation of the difference) of 0.28 (a modest treatment effect). To put this effect size in perspective, Patzkowski et al., reports effect sizes for FSST, TSA, SSWV-L and 40D of approximately 0.6, 0.7, 1.0 and 1.0, respectively.

Based on the above considerations, the targeted sample size for the study is 85 patients.

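### The Aim 3 device-satisfaction regression has no site term, although site-specific staff make and fit the brace, so patient-factor associations may be confounded by site (minor; inexpensive to fix)

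*Combined protocol and SAP*

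**What the plan says.** Section 10.6, under Specific Aim #3, names the explanatory variables of the satisfaction model: "variations in device satisfaction will be modeled as a function of patient characteristics and baseline measures of impairment". It adds only that suitable regression methods will be used. No site, centre or orthotist term appears anywhere in section 10.

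The same paragraph says "This aim is largely descriptive in nature", and the Protocol Summary says of Aim 3: "As this is primarily a descriptive analysis, no hypotheses will be tested".

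Section 7 places brace-making with local staff: "All braces will be fabricated by trained Certified Prosthetist/Orthotists (CPOs) at each participating MTF". On staffing it says: "The two participating study MTF sites will each identify 1-2 physical therapy assistants and 1 CPO and 1 O&P tech who will provide the services". The Protocol Summary and sections 4 and 5.1 give three sites, so the count of two in section 7 has to be reconciled with them. Staffing at the third site is not stated.

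Section 6.4.2 describes the OPUS as two measures, 11 items on the device and 10 on services. The device items include comfort, pain with use, durability and fit.

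**The concern.** Fit, comfort and durability plausibly depend on who measured, built and adjusted the brace, and those people differ by facility. Experience may differ too. Section 7.1 has the team that developed the device train the orthotists of the other two facilities in a 6-8 week internship, which implies, without stating it, that the third site is the originating centre.

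Patient mix may also differ by facility. Under section 5.2, recruitment draws on each centre's own registry, on referrals, and on local radio and newspaper advertising, and nothing balances patient type between centres.

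If both vary together, a model without site gives part of the site difference to whichever patient factor tracks it. Aim 3 could then describe certain patients as more or less satisfied when part of the difference lies between facilities. The programme is meant to be scaled beyond the originating centre, so satisfaction by site is useful in itself, and the plan does not ask for it.

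**Working it through.** **The plan's own figure.** The documents state no sample size or power for the Aim 3 model. The one stated figure, 80% power at a standardized effect of 0.28 with 80 completers (section 10.2), belongs to the paired tests of Aims 1 and 2. It reproduces: a one-sided paired t-test at 0.05 (alpha assumed, since none is stated) has 79.9% power. It has no bearing on this point.

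**Inputs from the documents.** 80 analysable participants and three sites, "approximately 25-30 from each center", taken as 27/27/26.

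**Assumed inputs.** A binary patient factor x with no true effect on satisfaction, its prevalence by site, and site mean shifts of −d, 0, +d in units of the within-site SD.

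**Formula.** With site omitted, the expected coefficient of x is Cov(site mean of x, site mean of satisfaction) / Var(x). For equal sites and prevalences of 0.5 − p, 0.5, 0.5 + p:

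- Cov = (2/3) × p × d
- Var(x) = 0.5 × 0.5 = 0.25
- spurious coefficient = (2/3) × p × d / 0.25

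**Results.** The rejection rates are simulated (OLS, two-sided 5%; 4,000 runs per scenario at 30/50/70%, 8,000 at 40/50/60%).

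| Prevalence by site | d | Spurious coefficient (formula) | Rejection, no site term |
|---|---|---|---|
| 30/50/70% (p = 0.2) | 0.25 | 0.133 SD | 8.1% |
| | 0.4 | 0.213 SD | 14.3% |
| | 0.5 | 0.267 SD | 20.3% |
| 40/50/60% (p = 0.1) | 0.25 | 0.067 SD | 6.0% |
| | 0.4 | 0.107 SD | 7.3% |
| | 0.5 | 0.133 SD | 8.6% |
| Equal (p = 0) | any | 0 | about 5% |

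The simulated coefficients agree: 0.13 to 0.27 SD in the first block and 0.07 to 0.14 SD in the second. At 45/50/55% rejection is 4 to 6%. At 30/50/70% with shifts of only ±0.1 SD it is 5.0%. With site indicators in the model at 30/50/70%, rejection is 4.6 to 5.1% and the bias is about zero.

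**Check with a continuous factor.** Let satisfaction and the factor differ between the extreme sites by D and M within-site SDs. The spurious standardized slope is (D × M / 6) / (1 + M²/6). For D = M = 0.5 this is 0.0417/1.0417 = 0.04. For D = M = 1.0 it is 0.1667/1.1667 = 0.143 (simulated 0.145). Simulated rejection runs from 5.8% to 24.4% over these cases. With M = 0 the slope is zero, and site differences only enlarge the residual variance.

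**Price of the site term.** At 30/50/70% the within-site variance of x is (0.21 + 0.25 + 0.21)/3 = 0.223, so the standard error grows by √(0.25/0.223) = 1.06 when sites do not in fact differ in satisfaction. When the factor is balanced and sites differ by ±0.5 SD, the term helps: the SD of the coefficient falls from 0.238 to 0.225, about 6%.

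**The case against.** The strongest reply is that this is a one-sentence description of a secondary, descriptive model with no hypothesis tests, so a false-positive rate is an awkward yardstick and the list of explanatory variables may not be exhaustive. The first part stands and limits the severity. It does not remove the point, because a fitted coefficient will be read with or without a p-value. On the second part, the reference to suitable regression methods concerns the type of model, not its covariates.

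Several stronger readings are tempting, and the documents do not support them:

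- A reader might infer that orthotist differences will be reported as patient effects. That requires both satisfaction and the factor to differ by site, and the documents give data on neither. The training in section 7.1, the physical therapy standardization in section 7.2 and the certification in section 11.2 may also narrow site differences.
- A reader might infer that a single orthotist makes and fits every brace at every site. Section 7 gives one CPO and one O&P technician to each of two sites and is silent on the third.
- A reader might lean on the service items: "Items used to measure satisfaction with services, include wait time, respect, communication". Those belong to the separate services measure, while the planned model is for device satisfaction. Among the device items, weight, cosmesis and ease of use may largely reflect a design common to all sites.
- A reader might infer that a site term would reveal an orthotist effect. Site is inseparable from orthotist, technician, therapy staff and facility. With about 27 per site, a pairwise difference of about 0.78 SD is needed for 80% power (two-sided 5%), so site means will be imprecise.
- A reader might fear that patient selection will be misdirected. Nothing in the documents uses Aim 3 to select patients.

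**Conclusion.** The point holds as a minor one. The model as described omits site, the outcome plausibly depends on site-specific staff, and associations with patient factors may therefore be confounded by site. The sizes in the brief rest wholly on assumed prevalences and site shifts: the bias is material only when imbalance and site differences are both sizeable, is small when either is modest, and is zero when the factor is balanced. The analyses of Aims 1 and 2 do not depend on this model.

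**What to change.** In section 10.6, Specific Aim #3, add one sentence: the device-satisfaction regression will include study site as a fixed factor with three levels, alongside patient characteristics and baseline impairment. Report satisfaction descriptively by site with confidence intervals, and state that site stands for orthotist, technician, therapy team and facility together and cannot isolate an orthotist effect. Reconcile the two sites in section 7 with the three stated elsewhere, and state the staffing at the third.

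The cost is the 2 degrees of freedom and the possible 6% loss of precision worked out above. Data already flow and are reported by centre (section 11.1), so no new data collection is needed.

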Following 2-4 weeks of home PT (T1), the participant will be fitted with the IDEO and engage in four weeks of Post-IDEO PT at the study center. During these 4 weeks, adjustments to the brace will be made and the participants will learn how to optimize the use of the brace.

At the end of the four weeks of post-IDEO PT (T2), performance testing will be repeated and overall satisfaction with the device assessed. The purpose of these assessments is to measure any immediate gains in function. Participants will then be formally ‘discharged’ from the PRIORITI program. They will be given the number of the Study Site Orthotist to call if any concerns arise with the IDEO and its fit. The costs associated with all visits to the orthotist during the 12 month follow-up period will be covered by the study.

At 6 months following the completion of the PRIORITI program (T3), participants will be contacted by the Study Coordinator and asked to participate in a brief interview by phone. The main purpose of this phone call is to keep participants engaged in the study and motivate them to come back to the hospital for the final visit at 12 months. We will also use this opportunity to ask them questions about their functioning, satisfaction with the brace and use of services (overall and specific to the IDEO). This interview will last about 15 minutes. During the call the he coordinator will remind the participant of the 12 month follow up visit. If the participant is living outside of the research site area, the coordinator will inform the participant that travel expenses can be covered for the 12 month follow up visit. (See appendix K).

At 12 months following the completion of the PRIORITI program (T4), participants will be asked to return to the Study Center to repeat the performance tests and self reported measures of outcome and satisfaction with the IDEO. Additional questions regarding use of services (overall and specific to the IDEO) will also be asked.

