6.3 Participant Follow up and Data Collection

The follow up visit schedule for this study will be closely related to the timing of brace fitting and PT participation. Follow up will occur immediately following post-IDEO PT (T2), 6 months following completion of all PT (i.e. post PRIORITI) (T3), and 12 Months post PRIORITI (T4). Each visit will have an interval of time surrounding the ideal date for the visit during which the visit may be completed and the data included in the trial database. This interval is approximately 1-2 weeks before or after the ideal date for a visit.

The data collected at follow-up are described below. These data are summarized in Appendix C.

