6.3.4 Participant Interviews at T3

- ALL ITEMS ASKED AT T2 PLUS:

- Short Musculoskeletal Function Assessment (SMFA)
- Veterans Health Survey (VR-12)
- Usual major activity status
- If working: Work Productivity (WPAI)
- Hospitalizations in past 6 months
- Use of Orthotic Services in past 6 months
- Use of PT/OT Services in past 6 months
- Use of other Services in past 6 months

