6.3.5 Participant Interviews at T4

- ALL ITEMS ASKED AT T3 PLUS:
- Income (past year)
- Health Insurance (current)
- Self Efficacy
- Multidimensional Scale of Perceived Support (MSPS)
- Activities- Paffenbarger Activity Scale (PPAQ)
- Brief Pain Inventory (BPI)
- Patient Health Questionnaire Dépression Scale (PHQ-9)
- Post Traumatic Stress Disorder using the PCL Checklist

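### A missed T3 phone call leaves half of the self-reported service-use window unrecorded, because T4 as listed repeats the 6-month recall and 10.6 has no rule for the gap

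*Combined protocol and SAP*

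**What the plan says.** Section 10.6 (Analysis Plan, Specific Aim #4) sets the target: "Difference in one-year cost for the PRIORITI group relative to standard of care will be evaluated based on difference in means", with bootstrap confidence intervals. Under Aim 4 in the Protocol Summary, the standard-of-care side is projected, not observed in a comparison group.

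The service-use items appear in the interview lists of section 6.3:

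- **T2** (6.3.3): device use and satisfaction, shoe wear and ambulatory aids. There is no service-use item, and Appendix C agrees.
- **T3** (6.3.4 Participant Interviews at T3): "Hospitalizations in past 6 months", "Use of Orthotic Services in past 6 months", "Use of PT/OT Services in past 6 months" and "Use of other Services in past 6 months".
- **T4** (6.3.5 Participant Interviews at T4): "ALL ITEMS ASKED AT T3 PLUS" a further list, none of which is a service-use question.

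At T3, participants are "asked to participate in a brief interview by phone" (section 4). On visit timing, section 6.3 says: "This interval is approximately 1-2 weeks before or after the ideal date for a visit".

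Section 10.6 does not say how the two recall periods are joined, what happens to the cost of someone not reached at T3, or how off-date visits are handled. Section 10.4 describes missing-data methods in terms of treatment effects and does not mention costs.

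**The concern.** A yearly total built from two 6-month recalls is complete only if both interviews take place. Because the T4 recall as listed does not lengthen when T3 is missed, a participant can attend the final visit and still have no interview data for the first half of the follow-up year.

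A missed T3 is foreseeable. Section 4 presents the call mainly as a way to keep people engaged, and the payment schedule under Retention covers T0, T1, T2 and T4 but not T3. The protocol uses longer recalls elsewhere: baseline service use and T4 income are both asked over a year.

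At stake is the PRIORITI side of the Aim 4 cost comparison. The comparator is projected, so under-recording would not cancel between two groups interviewed on the same forms. Section 10.6 also calculates a 12-month cost-effectiveness ratio only if PRIORITI's average cost is the greater, so the direction of an error could matter.

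**Working it through.** **Figures in the plan.** The documents give no figure for recall coverage or for missed T3 calls. Their one computed design figure, a detectable effect of 0.28 with 80 completers, is reproduced if alpha is one-sided 0.05 (an assumption, as alpha is not stated): (1.645 + 0.842)/√80 = 0.278, or 0.280 with the exact noncentral t. Nothing below changes it.

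**Inputs.** Recall of 26 weeks at T3 and at T4 (6.3.4 and 6.3.5, participant interviews). T3 and T4 at weeks 26 and 52 after T2, each with a window of about 1-2 weeks (6.3). 80 participants with complete follow-up (10.2). Assumed: the cost year starts at T2, since 10.6 does not give its start.

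**Step 1. Weeks covered by recall.** Each interview held at week *t* covers week *t* − 26 to week *t*.

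| Situation | T3 covers | T4 covers | Result over weeks 0-52 |
|---|---|---|---|
| Both on time | 0 to 26 | 26 to 52 | complete |
| T3 missed, T4 on time | none | 26 to 52 | 26 of 52 weeks missing (50%) |
| T3 missed, T4 2 weeks late | none | 28 to 54 | 28 of 52 weeks missing (54%) |
| T3 2 weeks early, T4 2 weeks late | −2 to 24 | 28 to 54 | 4-week hole |
| T3 2 weeks late, T4 2 weeks early | 2 to 28 | 24 to 50 | 4 weeks counted twice, 4 others uncovered |

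With a 1-week window, the hole or overlap at the join is at most 2 weeks. In every case with both interviews, the total recall is 26 + 26 = 52 weeks.

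**Step 2. Share of total cost for a person who missed T3.** Let *L* be the share of one-year cost known from logs or study payments, with self-reported cost even over the year. The share lost is 0.5 × (1 − *L*): 50% at *L* = 0, 37.5% at 0.25, 25% at 0.5 and 12.5% at 0.75. The documents do not give *L*; these values only show the range.

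**Step 3. Effect on the mean.** Let *p* be the proportion who miss T3 but attend T4 (assumed 5%, 10%, 20%).

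- Missing months counted as zero, use even over the year: understatement of mean self-reported service cost = 0.5 × *p* = 2.5%, 5%, 10%.
- Complete cases only: 80 × (1 − *p*) = 76, 72, 64 participants. With unchanged spread, the interval widens by 1/√(1 − *p*) = 1.026, 1.054, 1.118.
- Sensitivity to uneven use: if 60% or 70% of self-reported cost fell in months 0-6, the understatement at *p* = 10% would be 6% or 7% instead of 5%.

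**Step 4. After the change.** If T4 asks back to the last completed interview (T2 when T3 was missed), a missed T3 loses 0 weeks instead of 26, and there is no hole or overlap at the join. A T4 visit 2 weeks early or late then gives 50 or 54 weeks of recall, so totals need bringing to 52.

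**The case against.** The strongest reply has five parts.

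- **The T4 recall is inferred.** The interview sections are topic lists, section 4 gives no recall period for T4, and the forms listed as appendices are not in the reviewed text. The form may already ask about the time since the last contact. This stands: the form must be checked first.
- **Other sources exist.** A reader might infer that a missed T3 loses half of the one-year cost. The documents do not support that. Section 7.2 requires each PT session to be documented, Appendix C lists treatment logs kept by the orthotist and therapists, and section 4 has the study pay for orthotist visits during the 12 months. Some hospitalizations might also surface through medical records (13.1) or adverse-event recording (8.2.1). However, section 6.3 schedules no record review of service use at follow-up, so outside care is not reliably covered.
- **Off-date visits need not bias the mean.** A reader might take the 4-week hole or overlap as a bias. With both interviews done, the recall always totals 52 weeks, holes and overlaps go both ways, and under even use the expected total is unchanged. This stands: the effect is per-person error at the extremes of the window.
- **Nothing says missing months count as zero.** A reader might infer that the plan favours the programme. That would follow only from an analysis the plan does not describe. The 10.4 methods could be extended to costs, with T4 use as auxiliary data. They are not so extended in the text, and modelling is weaker than asking.
- **The stakes are limited.** Aim 4 is descriptive, with no hypothesis tested. This stands.

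**Conclusion.** The point holds for self-reported service use. On the recall as listed, a participant who misses T3 and attends T4 has no interview record of hospitalizations, outside orthotic or PT/OT care, or other services for months 0-6 after the programme: 26 of 52 weeks. Section 10.6 does not say what then happens to that person's yearly cost.

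The effect on the Aim 4 mean cannot be computed from the documents, which give no missed-T3 rate; the dropout figure of under 5% in 10.2 is a different quantity. The 2.5-10% understatement rests on three assumptions together: 5-20% missing T3, even use over the year, and missing months set to zero. The 64-76 complete cases rest on the first alone. Whether missed calls would be related to service use is also unknown.

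This is a worthwhile, inexpensive improvement to a descriptive aim. The primary endpoints, their tests and the sample size are not affected.

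**What to change.** 1. Check the recall wording on the T4 service-use form. If it is a fixed 6 months, replace it with: *since your last completed study interview on [date]*, with the date pre-filled from REDCap. For anyone who missed T3, this reaches back to T2.
2. Word the T3 items to run from the T2 date, and record the start and end dates of every recall period.
3. In 10.6, state that each self-reported total is scaled or truncated to 52 weeks (for example, multiplied by 52/50 or 52/54 when T4 is 2 weeks early or late), and that the 10.4 missing-data methods also apply to costs.

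The cost is a rewording of the T3 and T4 forms, one pre-filled date field and a short addition to 10.6. The downside is a longer, less accurate recall for the few who missed T3, which is still better than no interview data for those months.
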